Appendix 3 Criteria for evaluating relationship between adverse events and study treatment

UNRELATED

This category is applicable to an AE that meets the following 3 criteria:

1. It does not follow a reasonable temporal sequence from administration of the study drug, i.e. the time between the administration of study drug and occurrence of the event is not plausible. If the study drug was interrupted or stopped the event did not improve or disappear. (There are important exceptions when an AE does not disappear upon discontinuation of the study drug, yet study drug-relatedness clearly exists; e.g., (1) bone marrow depression, (2) tardive dyskinesias.). If the study drug was re-administered it did not reappear.
2. It does not follow a known pattern of the response to the suspected study drug or drugs of the same substance class.
3. It is judged to be clearly and incontrovertibly due only to extraneous causes such as the subject's clinical state, environmental or toxic factors, or other modes of therapy administered to the subject.

REMOTE

This category is applicable to an AE that meets the following three criteria:

1. It does not follow a reasonable temporal sequence from administration of the study drug, i.e. the time between the administration of study drug and occurrence of the event is not plausible. If the study drug was interrupted or stopped the event did not improve or disappear. If the study drug was re-administered it did not re-appear.
2. It does not follow a known pattern of the response to the suspected study drug or drugs of the same substance class.
3. It may readily have been produced by the subject's clinical state, environmental or toxic factors, or other modes of therapy administered to the subject.

POSSIBLE

This category is applicable to an AE that does not meet the criteria for "unrelated" or "remote", nor the criteria for "probable". An AE would be considered possible if, or when, for example:

1. It follows a reasonable temporal sequence from administration of the study drug (see also additional explanations above) or it follows a known pattern of the response to the suspected study drug or drugs of the same substance class.
2. It may or may not have been produced by the subject's clinical state, environmental or toxic factors, or other modes of therapy administered to the subject.

Note: If an event neither follows a plausible temporal relationship nor a known pattern of response but there is no alternative explanation for the event, this will usually be judged a possibly related event.

PROBABLE

This category is applicable to an AE that is considered, with a high degree of certainty, to be related to the study drug. An AE may be considered probable, if it meets the following 3 criteria:

1. It follows a reasonable temporal sequence from administration of the study drug, i.e. the time between the administration of study drug and occurrence of the event is plausible. If the study drug was interrupted or stopped the event did improve or disappear. (There are important exceptions when an AE does not disappear upon discontinuation of the study drug, yet drug-relatedness clearly exists; e.g., (1) bone marrow depression, (2) tardive dyskinesias.) If the study drug was re-administered it did re-appear.
2. It follows a known pattern of the response to the suspected study drug or drugs of the same substance class.
3. It cannot be reasonably explained by the known characteristics of the subject's clinical state, environmental or toxic factors, or other modes of therapy administered to the subject.

Regardless of the criteria mentioned above, reappearance of an event upon re-challenge will be regarded as strong evidence of probable relationship to study drug.

Appendix 4 Laboratory reference values and formulas

Impaired renal function or known significant renal disease, as evidenced by an estimated glomerular filtration rate

Kidney maturation in the neonate has been described in two European guidance documents.^{9,10} The key points are:

- Glomerular filtration matures faster than the tubular function. Both depend not only on age and maturational status but also on adverse factors occurring in the pre- and post-natal period, including for example intrauterine growth retardation or administration of nephrotoxic drugs to the mother and the neonate.
- Post-menstrual age (PMA) (gestational age [GA] + postnatal age) of the neonate is likely to be the best parameter of the ongoing neonatal maturation
 - There may be two-fold to four-fold difference in GFR values between premature and full-term newborns.
 - From 26 weeks of GA at birth to 34 weeks of PMA, the increase in GFR is limited because of incomplete nephrogenesis.
 - Birth triggers a dramatic increase in GFR. The GFR increases from 10 mL/min/1.73 m² at birth to 20 to 30 mL/min/1.73 m² after 2 weeks.
 - After the first month, serum creatinine remains stable during the first 2 years of life (under 44 µMol/L = 0.5 mg/dL in the full-term neonate).
- Serum creatinine is elevated in the first days of life reflecting maternal creatinine and a low intrinsic GFR.
- In premature neonates, the persistence of an elevated serum creatinine during the first weeks of life is the result of a transitory process of tubular creatinine reabsorption.
- To monitor renal function serum creatinine is used after the first week of life in full-term neonates and after 4 weeks in premature neonates. Before these times, intra-individual changes (related to post-menstrual age) in serum creatinine are used as a guide to renal function.

In addition, the following references must be considered:

- Schwartz¹¹ published the following modified formula (based on creatinine levels determined with the enzymatic method):
$$\text{eGFR (mL/min/1.73m}^2\text{)} = 0.413 \cdot \text{length (cm)} / \text{creatinine (mg/dL)}$$

⁹ EMA (2004) Discussion paper on the impact of renal immaturity when investigating medicinal products intended for paediatric use

¹⁰ CHMP, PDCO (2009) Guideline on the investigation of medicinal products in the term and preterm neonate

¹¹ Schwartz GJ, et al (2009) New equations to estimate GFR in children with CKD. *J Am Soc Nephrol* 20:629–37

- Laboratory normal ranges (enzymatic method):

	Creatinine (mg/dL)	
UZ Leuven	0.31 – 0.88 (< 1 month)	0.16 – 0.39 (1–12 months)
AZ Sint-Jan	0.24 – 0.85 (< 2 month)	0.17 – 0.42 (2–12 months)

Abitbol¹² reported creatinine levels of 0.68 ± 0.14 mg/dL during postnatal day 3–7 in 60 preterm infants (34±3 weeks). The same report presented a graph of eGFRs calculated with the modified Schwartz formula, in which the values of all age groups were greater than 20 mL/min/ 1.73 m². Of note, the creatinine-based equation underestimated the GFR compared to the CysC-based equations, especially in pre-term neonates.

- In the meropenem PK study published by Van den Anker¹³, a creatinine level of greater than 140 µmol/L (= 1.58 mg/dL) led to the exclusion of the subject from the study.
- Two graphs presented at an EMA Workshop on regulatory and scientific issues related to the investigation of medicinal products intended for neonate use¹⁴ indicated that creatinine levels in neonates of more than 1000 g body weight, or a GA of more than 27 weeks, fell from a maximum of about 110 µmol/L on day 1 to about 50 µmol/L within 3 to 4 weeks.

Conclusion

Serum creatinine levels are generally used to monitor renal function.¹⁰ GFR is indirectly proportional to creatinine, i.e. a GFR of 2/3 of normal corresponds to a 1.5-fold higher than normal creatinine level. Since PMA is the best parameter of kidney maturation, the following creatinine thresholds (determined with the enzymatic method) may be used to support the evaluation of exclusion criterion 5:

PMA (weeks)	Creatinine (mg/dL)	Rationale
28–34 completed	1.32	150% of the upper limit of the laboratory normal ranges
35–42 completed	1.1	Arithmetic mean of 1.32 and 0.88
> 42	0.88	Upper limit of the laboratory normal ranges of the lower age groups and slightly more than 150% of 0.5 mg/dL, the stable creatinine level during the first 2 years of life

¹² Abitbol CL et al (2014) Neonatal kidney size and function in preterm Infants: What is a true estimate of glomerular filtration rate? J Pediatr 164:1026-31).

¹³ Van den Anker JN, et al (2009) Meropenem pharmacokinetics in the newborn. AAC 53(9):3871

¹⁴ Van den Anker (2006) Workshop on Regulatory and Scientific Issues related to the Investigation of Medicinal Products intended for Neonatal Use

Considering these creatinine thresholds, a GFR estimated with the modified Schwartz formula of less than the values given below might provide evidence of impaired renal function or known significant renal disease:

Length (cm)	eGFR threshold (mL/min/1.73m ²)		
	Post-menstrual age (weeks)		
	38–34 completed	35–42 completed	> 42
33	10.3	12.4	15.5
34	10.6	12.8	16.0
35	11.0	13.1	16.4
36	11.3	13.5	16.9
37	11.6	13.9	17.4
38	11.9	14.3	17.8
39	12.2	14.6	18.3
40	12.5	15.0	18.8
41	12.8	15.4	19.2
42	13.1	15.8	19.7
43	13.5	16.1	20.2
44	13.8	16.5	20.7
45	14.1	16.9	21.1
46	14.4	17.3	21.6
47	14.7	17.6	22.1
48	15.0	18.0	22.5
49	15.3	18.4	23.0
50	15.6	18.8	23.5
51	16.0	19.1	23.9
52	16.3	19.5	24.4
53	16.6	19.9	24.9
54	16.9	20.3	25.3
55	17.2	20.7	25.8
56	17.5	21.0	26.3
57	17.8	21.4	26.8
58	18.1	21.8	27.2
59	18.5	22.2	27.7
60	18.8	22.5	28.2

Investigators will exercise their clinical knowledge in conjunction with these thresholds when determining the applicability of exclusion criterion 5 to individual patients.

C _{max}	Maximum observed plasma concentration
ITT	Intent-to-treat
IV	Intravenous
MIC	Minimum inhibitory concentration
PK	Pharmacokinetic(s)
SAE	Serious adverse event
SAP	Statistical Analysis Plan
t _{1/2}	Half-life
T > MIC	Time that concentration is above the MIC
V _{ss}	Volume of distribution at steady-state
WBC	White blood cell
RBC	Red blood cell

1 INTRODUCTION

This statistical analysis plan covers the detailed procedures for performing the statistical analyses and producing tables, listings and figures in the study described in Basilea Pharmaceutica International Ltd. (Basilea) Protocol BPR-PIP-001, version 5 dated 21st of March 2019..

2 STUDY OBJECTIVES, MAIN PARAMETERS AND DESIGN

2.1 Study Objectives

2.1.1 Primary objective

The primary objective of this study is to characterize the pharmacokinetics (PK) of a single dose of ceftobiprole in neonates and infants aged ≤ 3 months.

2.1.2 Secondary objective

The secondary objective of this study is to evaluate the safety and tolerability of ceftobiprole in neonates and infants aged ≤ 3 months.

2.2 Main Study Parameters

2.2.1 Efficacy

Not applicable for this study.

2.2.2 Safety and Tolerability

Adverse events, laboratory tests (hematology, biochemistry, urinalysis), vital signs, physical examination.

2.2.3 Pharmacokinetics

Non-compartmental analysis: C_{max} , $t_{1/2}$, AUC_{0-t} , $AUC_{0-\infty}$, CL_S , V_{SS} , $T > MIC$.

The relationship between exposure (C_{max} and AUC), derived PK parameters (CL_S , V_{SS} , $t_{1/2}$), gestational age, post-natal age, body weight, body mass index, body surface area, and calculated creatinine clearance will also be assessed.

2.3 Study Design

2.3.1 Study design and sample size

This is an open-label, single-fixed-dose, multicenter study carried out in three sequential cohorts. Each cohort consists of 15 neonates or infants aged ≤ 3 months (45 subjects total). The study will be conducted in European and United States centers.

No sample size calculation has been performed for this study. Study drug treatment of 15 subjects per dosing cohort (total $N = 45$) is based on experience and is considered sufficient to fulfil the objectives of this study.

The study comprises:

- I. A pre-dosing screening phase of up to 24 hours,
- II. A 1-day dosing phase with a single-dose intravenous administration of ceftobiprole at 7.5 mg/kg, and
- III. A post-dose follow-up safety assessment on Day 7 ± 3 after ceftobiprole administration.

2.3.1.1 Cohorts

The study population was initially planned to comprise of 3 cohorts, with 15 subjects in each cohort, based on gestational age (28 to 32 weeks [Cohort 3]; 33 to 36 weeks [Cohort 2]; ≥ 37 weeks [Cohort 1]).

Due to the very low rate of patient recruitment, only cohort 1 was successfully completed. There is no cohort 2 and cohort 3 population at the end of the study.

2.4 Assessments

The study assessments from screening to follow-up are summarized in Table 1 below:

Table 1: Schedule of assessments

	Screening Day -1 to 1	Dosing Day 1	Follow-up Day 7±3
SCREENING AND ADMINISTRATIVE PROCEDURES			
Written Informed consent ¹	X		
Inclusion/exclusion criteria	X		
Medical history	X		
Prior medications ²	X		
CEFTOBIPROLE ADMINISTRATION			
Infusion of ceftobiprole ³		X	
Collection of aliquot of infusion solution ⁴		X	
PHARMACOKINETIC PROCEDURES			
Blood sample collection ⁵		X	
Urine collection ⁶		X	
SAFETY PROCEDURES			
Vital signs ⁷	X	X	X
Physical examination	X	X*	X
Body weight and height ⁸	X	X*	X
Laboratory tests ⁹	X		X
Concomitant medication		X	X
Adverse events		< -----X----- >	

¹ Informed consent must be obtained within 3 days prior to dosing on Day 1.

² Prior medications administered within the 7 days prior to dosing will be collected.

³ Ceftobiprole must be administered via a separate infusion line. No other intravenous infusion may be given through the same line during the 4-hour ceftobiprole infusion, and – if feasible – attempts should be made to not simultaneously administer any other antibiotic treatment (i.e., through any infusion line) during the ceftobiprole infusion. If feasible, attempts should be made to allow for a minimum period of 30 minutes between the end of administration of any other antibiotic treatment and the start of ceftobiprole medocaril infusion.

⁴ An aliquot of approximately 3 mL of infusion solution will be collected after completion of the ceftobiprole infusion and frozen at below -65 °C immediately after sampling.

⁵ Blood samples of 200–300 µL will be obtained for PK analysis at the times described in Table 2.

6 Attempts should be made to obtain urine at the times described in Table 2; **NB:** Full portions of urine will be collected from subjects in whom a urinary catheter has been placed for their standard clinical care. Urinary catheters will not be placed for the purpose of the study. For subjects without a urinary catheter, one or more portions of urine may be obtained before, during, and after dosing.

⁷ Vital signs (body temperature, respiratory rate, pulse rate, and systolic and diastolic blood pressures) will be measured at the times described in Table 2.

⁸ Height must be recorded at screening only. The body weight determination on Day 1 will be used for dose calculation and should be obtained within 6-hours prior to dosing.

⁹ Safety laboratory tests include hematology, biochemistry, and urinalysis (see protocol Section 5.2.3.2).

*Physical examination and body weight obtained during the screening evaluation do not need to be repeated as Day 1 assessments if they were performed within 6 hours prior to dosing on Day 1.

The schedule of PK sampling and vital signs on Day 1 are summarized in Table 2 below:

Table 2: Schedule of PK sampling and vital signs on Day 1

Time	Vital signs	Blood samples	Urine collection *	Infusion solution aliquot collection
-2 to 0 h			X	
-15 min	X			
Pre-dose		X		
0 to 2 h			X	
1 h	X			
2 h		X		
2 h 15 min	X			
2 to 4 h			X	
4 h (end of infusion)		X		X
4 to 8 h			X	
6 h	X	X		
8 h		X		
8 to 12 h			X	
12 h		X		

* **NB:** Full portions of urine will be collected from subjects in whom a urinary catheter has been placed for their standard clinical care. Urinary catheters will not be placed for the purpose of the study. For subjects without a urinary catheter, one or more portions of urine may be obtained before, during, and after dosing.

2.4.1 Interim analyses

No hypothesis-testing interim analysis is planned. PK data from early dosing cohorts may be analyzed before dosing in later cohorts is started or completed. Safety data will be reviewed on an ongoing basis.

3 ANALYSIS POPULATIONS

3.1 Pharmacokinetics Population

Consists of all subjects who receive study drug and have adequate samples for determination of time-plasma concentration profiles of ceftobiprole. Subjects may be excluded from the PK analysis if they have significant protocol deviations, including eligibility criteria deviations, or if data which may influence the PK analysis are unavailable.

3.2 Safety Population

All subjects who receive any quantity of the study drug.

4 STATISTICAL CONSIDERATIONS AND ANALYSIS

4.1 General Considerations

No formal hypothesis testing will be performed. Summary outputs, where possible, will be presented for cohort 1.

4.3 Handling of Missing Data and/or Invalid Data and Outliers

Incomplete/partial dates will be replaced by derived variables and imputed using the following rules:

- if the day of the month is missing it is imputed to be the 15th if not in the month of study treatment. In case this leads to inconsistencies with other available patient's data, the imputation values will be handled case-by-case.
- if both the day and month are missing, they are imputed to be June 30 if not in year of study treatment. In case this leads to inconsistencies with other available patient's data, the imputation values will be handled case-by-case.
- missing years will be left as missing.
- missing times will be replaced by '00:00' for start times and '23:59' for end times if time is required.
- missing minutes will be replace by '00' for start times and '59' for end times times if time is required.

5 STATISTICAL PLAN AND METHODS

The statistical analysis will be performed using the software package SAS version 9.3 or higher (SAS Institute Inc., Cary, NC 27513, USA). Validation will be done by double programming.

All individual data as well as results of statistical analyses will be presented in individual patient data listings and statistical summary tables.

In general, continuous variables will be summarized using the following standard descriptive summary statistics: mean, standard deviation, median, minimum, maximum and number of observations. Categorical data will be described using frequency and percentage. Shift tables will be provided, where appropriate. One additional decimal point for mean, median, Q1, Q3 and two additional decimal points for SD will be used.

PK parameters will be presented by individual listings and descriptive summary statistics including arithmetic and geometric means, arithmetic and geometric coefficients of variation, standard deviation, minimum, median, and maximum.

Percentages will be rounded to one decimal place or more if most results are close to 0 or 100. Unscheduled assessments will only be listed and will not be included in the tables, unless otherwise specified. Any changes in the planned statistical methods will be documented in the clinical study report.

To assess the relationship between pairs of continuous variables (including PK parameters), the Pearson product moment correlation will be computed. This will however, only be applied when each variable has at least 5 non-missing observations. This correlation computation will apply to C_{max} , AUC, CL_s , V_{ss} , $t_{1/2}$, gestational and post-natal age, weight, BMI, BSA, and calculated creatinine clearance.

The following international dictionaries will be used for medical coding:

- Medical History events: MedDRA (version 20.1)
- Medications: WHO Drug Dictionary Enhanced (March 2018 B2 version)
- Adverse events: MedDRA (version 20.1)

Data from all participating study centers will be combined for analysis.

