3 mo	44.0	0.23	1.6	42.8	0.88	9	166.5	11.0	12	0.94

PNA = postnatal age; S_{cr} = serum creatinine; $T_{1/2}$ = half-life; AUC = area under the curve

Experience in paediatric subjects with other β -lactams

Numerous PK studies and population PK/PD analysis in paediatric subjects and neonates were conducted with meropenem. Depending on the infusion duration (0.5 h to 4 h) doses of 20 mg/kg to 40 mg/kg were predicted to be efficacious in full-term and pre-term neonates^{5,6,7}. These doses are similar to those investigated in infants with age > 2 months.

⁵ Padari. Short versus long infusion of meropenem in very-low-birth-weight neonates. *Antimicrob Agents Chemother.* 2012;56:4760-4

The present study will include full-term neonates and pre-term neonates. The creatinine clearance is reduced in pre-term neonates⁸. Therefore, a conservative approach is taken and a dose of 7.5 mg/kg 4-h infusion will be investigated in neonates and children age 3 months or below. This dose level of 7.5 mg/kg is considered to provide an adequate safety margin for subjects whose renal excretion capacity may be limited, and will allow for appropriate dose modeling to determine whether further dose stratification is required within the various groups of neonates, e.g. based on gestational or post-natal age, body weight, body surface area, creatinine clearance or other covariates.

⁶ Bradley. Meropenem pharmacokinetics, pharmacodynamics, and Monte Carlo simulation in the neonate. *Pediatr Infect Dis J.* 2008;27:794-9

⁷ Ohata. Optimal dosage regimen of meropenem for pediatric patients based on pharmacokinetic/ pharmacodynamic considerations. *Drug Metab Pharmacokinet.* 2011;26(5):523-31

⁸ van den Anker. Meropenem pharmacokinetics in the newborn. *Antimicrob Agents Chemother.* 2009;53(9):3871-9

Appendix 2 Collection, storage, and shipping of blood, plasma, infusion solution, and urine for pharmacokinetic analyses

Details on handling of PK samples are provided in the Pharmacokinetics Manual for this study (provided separately). The Pharmacokinetics Manual also contains instructions on shipping samples, including transport logistics. Materials needed for sampling will be provided by the sponsor.

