5.4.1.1 Pharmacokinetic analysis

Plasma concentrations at each time point of measurement will be evaluated by descriptive statistics, including arithmetic mean, standard deviation (SD), minimum, maximum, and median. Actual sampling times will be used to calculate PK parameters. If $\leq 50\%$ of the values at a given time point are BLQ, these values will be set to zero for mean value calculation. If more than 50% of the values at a given time point are BLQ, no mean value will be calculated. Mean plasma concentration profiles of cohort 1 will be generated according to these criteria.

For PK evaluation, BLQ-values at infusion start will be set to zero, BLQ-values at the end of the sampling period will be disregarded for PK assessment. Single BLQ values during blood sampling will be taken as 'missing values', if the following sample(s) show a concentration above the BLQ value.

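### Raw-scale Pearson correlation, the only association measure planned, tends to understate the inverse relations of AUC and half-life with creatinine clearance; log-scale and rank correlations should be added beside it

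*SAP*

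**What the plan says.** SAP section 5 names one measure for all pairs of continuous variables: "To assess the relationship between pairs of continuous variables (including PK parameters), the Pearson product moment correlation will be computed". The list covers Cmax, AUC, CLs, Vss, half-life, gestational and post-natal age, weight, BMI, BSA and calculated creatinine clearance. The only condition is that "each variable has at least 5 non-missing observations". No transformation, rank correlation, regression or plot is specified for these pairs. Protocol section 5.2.2.4 says only that the relationships will be assessed.

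The same SAP section summarises PK parameters by "arithmetic and geometric means, arithmetic and geometric coefficients of variation". Plasma concentrations (SAP section 5.4.1.1) get arithmetic statistics only: "including arithmetic mean, standard deviation (SD), minimum, maximum, and median".

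On sample size, SAP section 2.3.1 says "Each cohort consists of 15 neonates or infants", and section 2.3.1.1 reports that "only cohort 1 was successfully completed". The analysis therefore has about 15 infants.

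**The concern.** Pearson's r measures straight-line association. Several listed pairs are not straight lines on the raw scale. Protocol section 5.2.2.4 defines clearance as dose divided by AUC. Protocol Appendix 1 names creatinine clearance as the main driver of exposure. At a fixed mg/kg dose, AUC is then roughly proportional to the reciprocal of creatinine clearance, and half-life also falls as creatinine clearance rises. The raw-scale r for these pairs mixes the strength of the relation with the penalty for its curvature. CLs against creatinine clearance expresses the same biology without that penalty, so one relation can be reported at two strengths according to which reciprocal is tabulated.

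Protocol Appendix 1 says the chosen dose level "will allow for appropriate dose modeling to determine whether further dose stratification is required within the various groups of neonates", with age, size and creatinine clearance among the candidate covariates. A reader of the correlation table will look to it for a first view of those relations. The small sample adds a second weakness: one infant with unusually high exposure can move r a long way.

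**Working it through.** **No figure to reproduce.** The plan has no sample size calculation, no hypothesis test and no anticipated correlation. The check asks whether the inverse form is real, and how much r it costs.

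**1. Is the form reciprocal?** Protocol Appendix 1, Table 8 gives modelled AUC (µg·h/mL) and serum creatinine (mg/dL) in a normal and a worst case. If AUC is proportional to 1/creatinine clearance, the two worst-case/normal ratios should agree.

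| Post-natal age | AUC ratio | Creatinine ratio |
|---|---|---|
| 8 d | 189.3/63.2 = 3.00 | 1.10/0.38 = 2.89 |
| 15 d | 189.8/60.5 = 3.14 | 1.10/0.35 = 3.14 |
| 1 mo | 157.1/50.5 = 3.11 | 0.88/0.28 = 3.14 |
| 2 mo | 182.5/51.6 = 3.54 | 0.88/0.25 = 3.52 |
| 3 mo | 166.5/42.8 = 3.89 | 0.88/0.23 = 3.83 |

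They agree within 3.5%. Half-life is inverse too, but steeper than a plain reciprocal: its ratios run from 10/2.3 = 4.3 to 9/1.6 = 5.6.

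**2. Correlations on the Table 8 values**, with 1/creatinine standing in for creatinine clearance:

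| Rows | Pair | Raw r | Log-log r |
|---|---|---|---|
| Five normal | AUC | -0.963 | -0.951 |
| Five normal | Half-life | -0.970 | -0.955 |
| All ten | AUC | -0.955 | -0.993 |
| All ten | Half-life | -0.945 | -0.989 |
| All ten | Clearance per kg | 0.990 | 0.993 |

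Over the narrow normal range (CV of 1/creatinine about 21%) raw r is not the weaker one. Over the wide range it is, for the inverse pairs only. These rows are model values, not subjects, and the proxy ignores body length.

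**3. Simulation at n = 15.** Assumptions: creatinine clearance X is log-normal, CL = X × log-normal residual, AUC = 1/CL, 20,000 samples per setting. The documents give no distribution of creatinine clearance for Cohort 1, so the CVs are a range. Median r:

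| CV of X | Residual CV | AUC raw | AUC log-log | Loss | CL raw | Raw AUC weaker in |
|---|---|---|---|---|---|---|
| 20% | 20% | -0.70 | -0.72 | 0.02 | 0.72 | 74% |
| 20% | 30% | -0.55 | -0.58 | 0.02 | 0.56 | 69% |
| 30% | 20% | -0.79 | -0.84 | 0.05 | 0.83 | 87% |
| 30% | 30% | -0.67 | -0.72 | 0.05 | 0.71 | 82% |
| 50% | 20% | -0.81 | -0.93 | 0.12 | 0.92 | 98% |
| 50% | 30% | -0.74 | -0.86 | 0.12 | 0.85 | 95% |

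Losses are taken before rounding. The log-log r for CL equals that for AUC with the sign changed, so CL on the raw scale loses about 0.01. At 20% residual CV, the median Spearman correlation for AUC is -0.68, -0.80 and -0.90 at a CV of 20%, 30% and 50%. It exceeds raw Pearson in size at 30% and 50%, but not at 20%.

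**4. Hand check.** With g = 1 + CV² of X and h = 1 + CV² of the residual, the large-sample raw r for AUC is (1/g − 1)/√[(g − 1)(gh − 1)]. At CV 50% and residual 20%, g = 1.25 and h = 1.04, giving −0.20/√(0.25 × 0.30) = −0.73. The log-log value is −√[ln g/(ln g + ln h)] = −√(0.2231/0.2624) = −0.92. The direction agrees. The loss at n = 15 is smaller because so few infants seldom reach the tail where curvature is greatest.

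**5. Precision.** By Fisher's z, tanh(atanh r ± 1.96/√(n − 3)), the 95% interval around r = 0.8 is 0.49 to 0.93 at n = 15 and −0.28 to 0.99 at n = 5.

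**The case against.** Much of the case for leaving the plan alone stands.

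- A reader might infer that the strongest relations will be understated. The documents do not support this. The strongest relation they report is CLs with creatinine clearance (0.9858 in renally impaired subjects, Protocol Appendix 1). Both variables are on the correlation list, and that pair loses practically nothing.
- A reader might infer that the SAP contradicts itself by treating PK parameters as log-normal in the summaries and not in the correlations. It names no distribution; geometric statistics stand beside arithmetic ones.
- A reader might take the extreme case of an exact reciprocal, where r = −1/(1 + CV²) = −0.67 at CV 70%. That identity has no residual scatter, and nothing in the documents supports that CV.
- The spread may be modest. Adult PK variability is stated as below 30% (Protocol section 1.2.2.1), eGFR below two thirds of normal is excluded (section 4.3), and only the term cohort remains. Against this, the creatinine ranges in Protocol Appendix 4 (for example 0.31–0.88 mg/dL under 1 month and 0.16–0.39 at 1–12 months) are wide, and its supporting creatinine thresholds of 1.32, 1.1 and 0.88 lie at or above the upper limits of those ranges, so they trim little. Simulations built on those ranges, with assumed age mixes, gave creatinine-clearance CVs of 30–50% and losses of 0.04 to 0.11.
- A reader might infer that covariates will be ranked wrongly. No ranking is planned, and covariates compared within one PK parameter largely share its curvature. In a simulation with a noisier competing covariate (CV 30%, residual 20%), the true driver came first in 97.0% of samples on the raw scale and 97.1% on the log scale.
- Sampling error at n = 15 exceeds the loss at a moderate spread. True, but the loss has a consistent direction and is avoidable.

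**Conclusion.** The point holds in a limited form. For AUC and half-life against creatinine clearance, and AUC against CLs, raw-scale Pearson tends to understate the relation compared with the direct pair of CLs and creatinine clearance. The size, calculated for AUC against creatinine clearance, is about 0.02–0.05 in r at a creatinine-clearance CV of 20–30%, and about 0.12 at 50%. This rests on n = 15, log-normal inputs and a residual CV of 20–30%, all assumed except n. That the raw scale is meant is read from the SAP's silence on transformation. AUC is an exact reciprocal only of clearance per kg, since dose scales with weight, so the AUC–CLs pair will be somewhat looser than an identity.

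The separate weakness, that one extreme value can dominate r among 15 infants or as few as 5, holds whatever the spread.

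No primary conclusion changes. The primary variables are Cmax, AUC and time above MIC, no hypothesis is tested, individual values are listed, and PK parameters are also to be determined by post-natal age (Protocol section 5.2.2.4). Nothing says that the later dose modelling takes these coefficients as input. This is a worthwhile refinement, not an error.

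**What to change.** In SAP section 5, keep the planned raw Pearson correlations and add for the same pairs:

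- Pearson correlation with PK parameters, weight, BSA and creatinine clearance log-transformed, stating which variables stay untransformed (gestational and post-natal age, BMI), so that log-log and semi-log coefficients are labelled as such;
- Spearman's rank correlation, which limits the pull of a single extreme value;
- a scatter plot for each pair of interest;
- a 95% confidence interval and the number of pairs with each coefficient.

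Keeping the raw version matters, because it suits the near-linear pair of CLs and creatinine clearance. The cost is a few sentences of SAP text, some programming, and a few more table columns and figures. No new data are needed.
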